# 2.2. Efficacy Outcomes

As listed in the protocol (Section 5.6 Trial Assessments), the following efficacy outcomes will be analyzed or summarized depending on the amount of data collected:

- Visual acuity (VA)
- Contrast sensitivity
- Reading assessments
- Color vision assessments
- Static perimetry
- Full field stimulus testing (FST)
- Ocular examination
- Fundus photography
- Spectral domain optical coherence tomography (SD-OCT)
- Adaptive optics imaging
- Fundus autofluorescence
- Photoaversion (PA)
- Electroretinography (ERG)
- Quality of life (QoL) as measured by the Impact of Visual Impairment (IVI) questionnaire adult (IVI-A) and child (IVI-C) versions, and the EQ5D-5L and EQ5D-Y
- Photoaversion questionnaire.

#### 3. ANALYSIS DEFINITIONS

## 3.1. Analysis Sets

For safety analyses, the safety analysis set includes all enrolled participants who were administered ATIMP.

For efficacy analyses, the full analysis set includes all enrolled participants who were administered ATIMP and have both a baseline and data from at least 1 visit after ATIMP administration.

#### 3.2. Baseline

In general, baseline is defined as the closest visit prior to ATIMP administration and will exclude any screening observations (unless there are no other observations prior to ATIMP administration). However, for efficacy parameters with multiple planned assessments in the baseline window, the arithmetic mean will be used as the baseline value.

## 3.3. Study Day/Relative Day

For the purpose of the statistical analysis and reporting, Study Day 1 or Day 1 refers to the day of ATIMP administration. All efficacy and safety assessments at all visits will be assigned a day relative to this date.

Study day (or relative day) for a visit is defined as:

- Visit date (date of Study Day 1) +1 day, if the visit date is on or after Day 1
- Visit date date of Day 1, if the visit date is before Day 1

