### 5.4.2.3 Subsequent Assessments

On the first postoperative day a full clinical ocular examination will be performed. In particular, visual acuity, intraocular pressure, the degree of postoperative intraocular inflammation and the area of any

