## **Gene Therapy for Achromatopsia (CNGA3)**

---

residual retinal bleb will be documented. Fundus photography, autofluorescence imaging, ocular examination, intraocular pressure and SD-OCT will be performed at day 1 and each subsequent visit post ATIMP administration.

A standard post-vitrectomy treatment regimen of topical antibiotic (chloramphenicol 0.5% qds for 7 days) and steroid (dexamethasone 0.1% qds for 4 weeks) will be prescribed to minimise inflammation and protect against infection postoperatively.

Intraocular pressure of greater than 30 mmHg will be managed with topical medication and systemic therapy where indicated, with specialist advice sought as required.

Participants will be maintained on oral prednisolone (or other as appropriate) for 4 weeks following administration of ATIMP as described above (Section 5.4.2.2.1: Pre-operative procedure). The possible development of steroid-induced adverse effects will be monitored regularly. In particular, blood pressure will be measured and blood glucose, renal function and liver function will be evaluated through blood biochemistry at the time points specific in Table 2: Trial Assessments.

Both safety and efficacy of the ATIMP will be evaluated at various time points up to 6 months after ATIMP delivery. Evaluations will comprise primarily, ocular assessments. The nature and schedule (Section 5.6: Trial Assessments) of these is described below.

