### **(iii) Evaluation of biodistribution**

Systemic biodistribution of vector genomes will be assessed by PCR analysis of tears (a compressed cellulose sponge placed under the eye lid until swollen), saliva (a minimum of 100 µL) and serum (1 mL) at 1 day and at 4 weeks following intraocular ATIMP administration. The test will be carried out at a laboratory approved by the sponsor and their research development partners.

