**CNGA3CNGA3 Gene Therapy trial for Achromatopsia**

	Screening	Baseline 			ATIMP admin	D1	D3	W1	W2	W4	W6	W12	W24
Flexibility of schedule ( $\pm$ days)		- 9 months			Day 0	$\pm$ 0D	$\pm$ 1D	$\pm$ 2D	$\pm$ 4D	$\pm$ 7D	$\pm$ 7D	$\pm$ 14D	$\pm$ 14D
Fundus photography		•				•	•	•	•	•	•	•	•
Optical coherence tomography	•	•	•	•		•	•	•	•	•	•	•	•
Adaptive optics imaging		•	•										•
Fundus autofluorescence		•	•									•	•
Pattern Electroretinography 	•												•
Full field Electroretinography 	•												•
Photoaversion/ light sensitivity assessments (test and questionnaires)		• 	• 	• 								• 	• 

 Baseline assessments may be performed on the same day where considered logistically and clinically appropriate

 If result is available from prior testing, no repeat test mandated. Result will be reported into the CRF.

 Measurements for vital signs include: blood pressure, pulse, respiration rate, arterial oxygen saturation, temperature, height and weight

 Hematology to include the following parameters: Haemoglobin, Haematocrit, Erythrocytes, Mean Corpuscular Volume, Mean Corpuscular Haemoglobin, Platelet, Leukocytes, Absolute Neutrophils, Absolute Lymphocytes, Absolute Neutrophils, Absolute Eosinophils, Absolute Basophils

 Biochemistry to include the following parameters: Sodium, Potassium, Chloride, Bilirubin, Alkaline Phosphatase, Aspartate Aminotransferase, Alanine, Aminotransferase, Lactate Dehydrogenase, Gamma Glutamyl Transferase, Total Protein, Albumin, Calcium, Magnesium, Phosphate, Urea/BUN, Urate, Creatinine, Glucose

 Visual acuity at day 1 and 3 will be assessed using the previous refraction.

 ERG assessments may be performed under general anaesthesia if necessary.

 Photoaversion Questionnaire only to be completed at one baseline visit, "Photoaversion Device Questionnaire – Baseline" to be completed after every PA assessment

 "Photoaversion Device Questionnaire – after Surgery" to be used at week 12 and week 24 straight after Photoaversion assessments.

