#### 3.4. Visit Windows

The following rules are applied to assign actual visits to analysis visit windows other than baseline. If a participant has two or more actual visits in 1 visit window, the visit closest to the target day will be used as the protocol visit for that visit window. The additional visit(s) will not be used in the summaries or analyses, but they can be used for determination of clinically important outcomes. If two actual visits are equidistant from the target day within a visit window, the later visit is used. All assignments will be made in chronological order. Once a visit date is assigned to a visit window, it will no longer be used for a later time point.

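### SAP Table 1 mixes two day counts, so the first-postoperative-day visit falls in the 'Day 3' window with the protocol's D3 visit and one of the two drops out of by-visit summaries

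*SAP*

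**What the plan says.** **SAP.** Section 3.3 fixes the count: "Study Day 1 or Day 1 refers to the day of ATIMP administration". For later visits it takes the visit date minus the date of Study Day 1 and adds "1 day, if the visit date is on or after Day 1". There is no Day 0. In Section 3.4, Table 1, the 'Day 1' window is Study Day 1 alone (target 1), 'Day 3' is Study Days 2 to 5 (target 3) and 'Week 1' is Study Days 6 to 10 (target 8). The later targets are 15, 29, 43, 85 and 169. If two visits share a window, "the visit closest to the target day will be used as the protocol visit for that visit window". For ties, "If two actual visits are equidistant from the target day within a visit window, the later visit is used". A visit not selected is left out of summaries and analyses but may still be used to determine clinically important outcomes.

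**Protocol.** Table 2 (Section 5.6) places ATIMP administration at Day 0, followed by separate visits D1 (±0 days) and D3 (±1 day). Section 5.4.2.3 shows that D1 is the day after surgery: "On the first postoperative day a full clinical ocular examination will be performed". Imaging and ocular assessments "will be performed at day 1 and each subsequent visit post ATIMP administration", and PCR samples are taken "at 1 day and at 4 weeks following intraocular ATIMP administration". A footnote to Table 2 confirms that D1 and D3 each carry an acuity measurement: "Visual acuity at day 1 and 3 will be assessed using the previous refraction".

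**The concern.** The two documents number the days around surgery differently. That is harmless if the SAP converts every visit, but Table 1 appears to convert the week rows and not the two day rows. If so, the visit the protocol calls D1 cannot enter the row the SAP calls 'Day 1', and it competes with D3 for a single place.

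At stake is the by-visit description of the first days after subretinal surgery, in a trial whose primary objective is safety. A 'Day 1' row with no postoperative data, and a 'Day 3' row holding first-day values for some participants and later values for others, would misdescribe early acuity, inflammation, intraocular pressure and retinal structure.

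**Working it through.** **Inputs.** SAP count: surgery = Study Day 1 (SAP 3.3). Protocol count: surgery = Day 0, with visit days and tolerances from Table 2. Windows, targets and selection rules: SAP 3.4 and Table 1.

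**Step 1: reproduce the SAP targets.** Study day = postoperative day + 1.

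| Visit | Protocol day (tolerance) | Study day expected | SAP target | Difference |
|---|---|---|---|---|
| D1 | 1 (±0) | 2 | 1 | −1 |
| D3 | 3 (±1) | 4 | 3 | −1 |
| W1 | 7 (±2) | 8 | 8 | 0 |
| W2 | 14 (±4) | 15 | 15 | 0 |
| W4 | 28 (±7) | 29 | 29 | 0 |
| W6 | 42 (±7) | 43 | 43 | 0 |
| W12 | 84 (±14) | 85 | 85 | 0 |
| W24 | 168 (±14) | 169 | 169 | 0 |

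The six week targets reproduce exactly. The two day targets are each one day too low. The Week 1 limits confirm the convention: 7 ± 2 gives postoperative days 5 to 9, and adding 1 gives Study Days 6 to 10, as printed.

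**Step 2: place the two early visits.** D1 is always 1 + 1 = Study Day 2. D3, on postoperative days 2 to 4, is Study Days 3 to 5. Both lie wholly inside the 'Day 3' window of Study Days 2 to 5. The 'Day 1' window contains only the day of surgery, for which Table 2 schedules no acuity, ocular examination, imaging, laboratory test, vital signs or PCR.

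**Step 3: apply the selection rules when both visits take place.** D1 is at distance |2 − 3| = 1 from the target.

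| D3 held on postoperative day | Study day of D3 | Distance of D3 | Kept as 'Day 3' | Excluded |
|---|---|---|---|---|
| 2 | 3 | 0 | D3 | D1 |
| 3 (on schedule) | 4 | 1 (tie, later visit used) | D3 | D1 |
| 4 | 5 | 2 | D1 | D3 |

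If D3 is missed, D1 alone is in the window and is reported as 'Day 3'.

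**Step 4: try the other convention.** Reading Table 1 with surgery as Day 0 contradicts SAP 3.3. It places D1 and D3 correctly, but every week target is then one day too high, and visits inside protocol tolerance go astray: W1 on postoperative day 5 falls in 'Day 3', and W2 on day 10 falls in 'Week 1'. Neither count makes the whole table work.

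**Step 5: identify the data affected (Table 2).** Acuity, ocular examination, fundus photography and OCT are scheduled at both D1 and D3, so they collide. Haematology, biochemistry and vital signs are scheduled at D1 but not D3. If selection is by visit, as SAP 3.4 is worded, these D1 results drop out whenever D3 is selected. If selection is by parameter, they survive under the label 'Day 3'. PCR is also taken at D1 and not D3, but SAP 5.3 says only that it is summarised by tissue, so the effect depends on whether that summary is by visit.

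**The case against.** The best defence accepts the date mapping and disputes its consequences. Most of that defence stands.

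- **Early safety data are not lost to the trial.** A reader might infer that they are. SAP 3.4 lets unselected visits be used for clinically important outcomes. The primary safety outcome (SAP 2.1, 5.1) counts qualifying events over 6 weeks, and the adverse-event tables (SAP 5.2) count all treatment-emergent events; neither is windowed. Protocol 5.11.3.5 requires clinically significant test abnormalities to be recorded as adverse events. SAP 5.3 lists all haematology, chemistry and PCR values.
- **Not every by-visit table is affected.** In Table 2, contrast sensitivity, colour vision, reading, perimetry, full-field stimulus testing and photoaversion are first repeated after surgery at W12, and adaptive optics, ERG and quality of life at W24. They have no Day 1 entry to lose.
- **Not every participant loses a visit.** Any D1 visit held on schedule is misplaced, but a visit is excluded only if D3 also took place. The COVID-19 appendix allows follow-up visits to be replaced by telephone contact.
- **The early acuity values carry less weight for efficacy.** D1 and D3 acuity uses an earlier refraction, and the protocol summary assesses efficacy between 3 and 6 months.

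Two replies do not stand. SAP 3.4 assigns actual visits to windows by study day, so programmers cannot simply fall back on nominal visit names. Assigning visits in chronological order does not help either, because Study Day 2 lies outside the 'Day 1' window.

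**Conclusion.** The point holds for by-visit summaries and no further. Followed as written, Table 1 gives wrong early rows even when every visit is on schedule: no postoperative data under 'Day 1', and D1 excluded in favour of D3. With D3 one day late, D1 is shown as 'Day 3' and the real D3 is excluded. Across participants who attend both visits within tolerance, the 'Day 3' row can mix values from postoperative days 1, 2 and 3.

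The collision covers acuity, ocular examination, fundus photography and OCT. For D1 haematology, biochemistry and vital signs, the SAP does not settle whether results are dropped or relabelled. Listings, the primary safety outcome, adverse-event tables and Week 12 and 24 results are not affected, and the documents do not support a claim that the safety conclusion would change. The analysis is descriptive with no formal hypothesis testing (SAP 1.2), which also limits the weight of the point. It should be corrected because the table contradicts its own day count.

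This rests on D1 being the first postoperative day, which the protocol states, and on D3 being held within its ±1 day tolerance.

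**What to change.** In SAP Table 1:

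- set 'Day 1' to Study Day 2, target 2;
- set 'Day 3' to Study Days 3 to 5, target 4;
- label Study Day 1 as 'ATIMP administration'.

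Check: D1 (Study Day 2) then always maps to 'Day 1', and D3 on postoperative days 2, 3 or 4 (Study Days 3, 4 or 5) always maps to 'Day 3'. The two never share a window when held within protocol tolerance, and neither is excluded. The week rows do not need to change for this.

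It would help to state in the same edit whether selection within a window is by visit or by parameter, and whether the PCR summary is by visit.

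The cost is two table rows, one label and the matching programming. No assessment, visit or clinical procedure changes.

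A separate, minor point can be checked at the same time: a W6 visit on its earliest permitted day, postoperative day 35, is Study Day 36 and falls in the 'Week 4' window.

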#### 3.4. Visit Windows

The following rules are applied to assign actual visits to analysis visit windows other than baseline. If a participant has two or more actual visits in 1 visit window, the visit closest to the target day will be used as the protocol visit for that visit window. The additional visit(s) will not be used in the summaries or analyses, but they can be used for determination of clinically important outcomes. If two actual visits are equidistant from the target day within a visit window, the later visit is used. All assignments will be made in chronological order. Once a visit date is assigned to a visit window, it will no longer be used for a later time point.

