**Gene Therapy for Achromatopsia (CNGA3)**

section 5.4.2.1 for details) to allow direct comparison of the data sets. These assessments will be scheduled over a period of a day for visits at day 1, day 3, day 7, week 2, week 4 and week 6 after surgery, and up to 4 days for baseline examinations, and 3 months, 6 months following ATIMP administration. For day 1 and 3 refraction cannot reliably be measured. Therefore, the most recent refraction measurement will be used.

All participants will need to be able to perform reliable visual acuity testing and SD-OCT imaging, which are the principal clinical assessments both for safety and efficacy. Other clinical assessments will be undertaken as appropriate for the ability of individual participants, since there is wide variation in the abilities of individual children to perform such tests reliably; the evaluations for individuals may be restricted to those tests that they are able to perform reliably.

Additional assessments may be performed if considered appropriate for the management of any unexpected adverse effects. These may be submitted as urgent safety measures and protocol amendments performed where required. Conversely, tests that cannot be reliably performed by a particular participant may be discontinued for that participant. This is not anticipated for the key clinical assessments such as visual acuity test or SD-OCT imaging because participants who are unable to perform such tests will be excluded from the study at the screening phase. Evaluation of safety and efficacy will also be performed on an individual participant basis. We do not anticipate that any discontinuation will affect significantly the overall quality of the safety and efficacy evaluation.

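### SAP 3.4 selects one whole visit per window instead of one result per test, so scheduled results can drop out of the summaries, including the day 1 laboratory results under full compliance

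*SAP*

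**What the plan says.** SAP 3.4 sets the rule. With two or more actual visits in a window, "the visit closest to the target day will be used as the protocol visit for that visit window". For the others, "The additional visit(s) will not be used in the summaries or analyses", although they may still serve for deciding clinically important outcomes, a term that the SAP does not define. Ties are settled in favour of the later date: "If two actual visits are equidistant from the target day within a visit window, the later visit is used". Assignment works on visit dates: "Once a visit date is assigned to a visit window, it will no longer be used for a later time point". The section has no rule by parameter, no preference for scheduled over unscheduled visits, and no provision for a visit that extends over several dates. Baseline is treated differently: SAP 3.2 averages multiple planned efficacy assessments.

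SAP 3.3 numbers the day of administration as Day 1, whereas Protocol Table 2 calls it Day 0. SAP Table 1 gives these windows:

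- Day 1: Day 1 only
- Day 3: Days 2 to 5, target Day 3
- Week 12: Days 60 to 127, target Day 85
- Week 24: Day 128 onward, target Day 169

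Protocol 5.4.2.3 gives one day to each visit up to week 6, but "up to 4 days for baseline examinations, and 3 months, 6 months following ATIMP administration". It also allows for unplanned testing: "Additional assessments may be performed if considered appropriate for the management of any unexpected adverse effects". The COVID-19 appendix lets a site arrange an additional visit when a window is missed.

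**The concern.** The visits are not interchangeable. Table 2 schedules different tests at different time points, and an extra visit for an adverse effect may include only a few of them. A rule that keeps one visit and sets aside the rest therefore removes any test that the retained visit did not include, even when a valid result exists a few days away.

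Little data is available to absorb such a loss:

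- PCR is scheduled only at D1 and week 4.
- D1 is one of the times at which Protocol 4.1.5.6 says blood pressure, glucose, renal and liver function are checked for steroid effects.
- ERG, adaptive optics and quality of life have week 24 as their only post-treatment assessment.
- Colour vision, contrast sensitivity, reading, static perimetry, FST and photoaversion have only weeks 12 and 24. Protocol 5.5.2 asks for an improvement in visual function sustained over at least two consecutive assessments, which these tests cannot show if either battery is missing.
- Cohorts start at 3 participants, so one lost battery is 1/3 of a dose level for that time point.

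**Working it through.** The plan gives no figure of its own to reproduce. The check applies the SAP 3.4 rule to the Protocol Table 2 schedule.

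**Day conversion.** SAP day = protocol day + 1. The targets in SAP Table 1 follow this from week 1 on: 7+1 = 8, 14+1 = 15, 28+1 = 29, 42+1 = 43, 84+1 = 85, 168+1 = 169. The two earliest rows do not. Protocol D1 is SAP Day 2 and protocol D3 is SAP Day 4, but the SAP targets are Day 1 and Day 3.

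**(a) D1 and D3 with full compliance.** D1 has a tolerance of 0 days, so it is SAP Day 2. D3 has a tolerance of 1 day, so it is SAP Day 3, 4 or 5. All these dates lie in the SAP Day 3 window (Days 2 to 5, target 3). D1 is |2 − 3| = 1 day from target.

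| D3 on SAP day | Distance of D3 | Kept | Dropped |
|---|---|---|---|
| 3 | 0 | D3 | D1 |
| 4 (nominal) | 1, a tie | D3, as the later | D1 |
| 5 | 2 | D1 | D3 |

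When both visits take place, one is always dropped, and on the nominal schedule it is D1. Table 2 has haematology, biochemistry, vital signs and PCR at D1 but not at D3, so these leave the by-visit summaries. Acuity, ocular examination, fundus photography and OCT are done at both visits, so one of the two results goes. The SAP Day 1 window contains only the day of surgery, when Table 2 schedules none of these tests. For PCR, the outcome also conflicts with SAP 5.3, which promises a summary of every PCR value.

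**(b) Displacement by an extra visit.**

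- Week 12: permitted dates are SAP Days 71 to 99 (85 ± 14). Take a battery on Day 78, |78 − 85| = 7, and an extra visit on Day 84, |84 − 85| = 1. Day 84 is kept and the battery is excluded.
- Week 24: permitted dates are SAP Days 155 to 183 (169 ± 14). Take a late battery on Day 180, |180 − 169| = 11, preceded by an extra visit on Day 172, |172 − 169| = 3. Day 172 is kept and the battery is excluded.

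**(c) Batteries over several days.** Table 2 lists 11 efficacy tests at week 12 and 15 at week 24. There are two ways to record a 4-day battery:

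- Under one visit number: nothing competes, and 11 of 11 and 15 of 15 are kept.
- Each date as its own visit: Days 84 to 87 reduce to Day 85, and Days 168 to 171 to Day 169. Assuming an even spread of tests over the 4 days, 11/4 = 2.75 and 15/4 = 3.75 tests are kept, about 3 of 11 and 4 of 15.

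The documents do not say which applies, so the loss in (c) ranges from none to about three quarters of the battery.

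**The case against.** Several points count against a stronger reading.

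- A reader might infer that the 4-day batteries will lose most of their tests. The documents do not support that. SAP 3.4 applies only when there are two or more actual visits, and Table 2 gives weeks 12 and 24 one visit number each, so a battery may well count as one visit. This stands, and (c) is only conditional.
- A reader might infer that extra adverse-event visits are expected. The protocol only permits additional assessments and gives no rate. This stands. Such visits would tend to occur in participants with problems, so the loss need not be random, but its size cannot be estimated.
- A reader might infer that an early week 24 battery, say on Day 155, is exposed to any attendance up to Day 183. Arithmetically it is, but Protocol 5.6.3 ends each participant's trial at the last scheduled visit, so a later attendance would ordinarily fall outside the trial. This stands, and only an extra visit that precedes a late battery is used in (b).
- A reader might infer that excluded visits are lost for every purpose, including the primary safety outcome. SAP 3.4 lets them serve for clinically important outcomes, and SAP 5.3 lists all haematology and chemistry values. This stands for those uses. The exception is undefined, however, and returns nothing to the summary tables or to the optional repeated-measures model in SAP 6.1.
- SAP 1 puts programming instructions in a separate document, and SAP 3.3 assigns a study day to assessments, so selection by parameter may be intended. That may be so, but SAP 3.4 as written selects visits, and a programming instruction should not have to contradict it.

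The trial is descriptive with no hypothesis test, so no error rate is at stake. None of this removes (a), which needs no extra visit and no assumption about multi-day recording.

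**Conclusion.** The concern holds in a limited form. Followed literally, SAP 3.4 drops one of the two earliest scheduled post-operative visits whenever both take place. On two of the three permitted D3 dates, including the nominal one, it drops D1 with four sets of measurements that D3 does not repeat. This assumes that the by-visit safety summaries use the SAP 3.4 windows, which SAP 3.3 and 3.4 imply by covering safety as well as efficacy assessments.

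Displacement of a week 12 battery, or of a late week 24 battery, is possible under the rule but depends on an extra visit that is only permitted. Loss from multi-day batteries is possible but depends on how visits are recorded. What is affected is the summaries and any model. The listings and the determination of clinically important outcomes are not shown to be affected.

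**What to change.** Amend SAP 3.4 so that selection is made separately for each parameter, from non-missing results only, in this order:

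1. Treat all dates of one numbered scheduled visit as one visit.
2. Prefer a scheduled result to an unscheduled one.
3. Then take the result closest to the target day.

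The order matters, because an unscheduled acuity nearer the target would otherwise leave steps 2 and 3 in conflict.

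Also align the first two rows of SAP Table 1 with the protocol day count: protocol D1 at SAP Day 2, and protocol D3 at SAP Days 3 to 5 with target Day 4. Selection by parameter alone would restore the D1 laboratory, vital-sign and PCR results, but tests done at both visits would still compete for one window.

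With these changes both early visits are kept, the Day 78 battery in the example is kept over the Day 84 visit, and a 4-day battery keeps 11 of 11 tests at week 12 and 15 of 15 at week 24. The cost is a few sentences in SAP 3.4, two rows of Table 1 and a programming note. No new data and no change to the visit schedule are needed.
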